7.4. Deaths and Other Serious Adverse Events

Deaths and other SAEs will be tabulated following the same pattern than AEs.

8. OTHER ANALYSES

Continuous variables will be tabulated and presented with summary statistics (i.e., mean, StD, median and range).

Categorical variables will be summarized in frequency tables by means of counts and percentages. Percentages in the summary tables will be rounded and may therefore not always add up to exactly 100%.

8.1. Patient Disposition and Treatment/Study Discontinuation

The number of patients included in the study, the number of patients treated and the number of patients evaluable for the main endpoint will be shown. Also, accrual by center and country and the main dates of the study will be displayed. Reasons for treatment discontinuation and for study discontinuation will be tabulated.

8.2. Protocol Deviations

Analysis of deviations regarding patients' eligibility, retreatment restrictions, concomitant medication and clinically relevant discontinuations, among others, will be done as described in Appendix I.

8.3. Baseline and Demographic Data

Baseline data such as demographics, cancer history, prior therapy, prior relevant history, signs and symptoms, electrocardiogram, LVEF, physical examination, vital signs, laboratory values and concomitant medication, coded according to the World Health Organization (WHO) Anatomical Therapeutic Chemical (ATC) classification system, will be described following standard tables detailed in Appendix I.

Age, baseline weight, height, and BSA values will be summarized descriptively. Age categories, race and baseline ECOG PS score will be summarized with frequency counts.

Baseline weight and height are recorded on the Case Report Form (CRF). If BSA value is missing, it will be calculated using the Dubois & Dubois formula:

$$BSA(m^2) = 0.007184 \times weight(kg)^{0.425} \times height(cm)^{0.725}$$

For the cancer history, time from initial diagnosis, time from metastatic disease and time from last progression before the study entry will be summarized. This time calculations will be shown in months and summarized descriptively. Histology and other characteristics of the primary and current disease will be described using standard tables detailed in Appendix I.

Previous relevant medical history (other than cancer) will be tabulated by SOC and PT.

A frequency tabulation of the number of patients with the different types of previous surgery, radiotherapy, or therapy (number of lines) will be given.

Signs and symptoms, defined as AEs reported at baseline, will be displayed by tabulation of frequencies according to NCI-CTCAE v.4 toxicity grades. Signs and symptoms will be listed.

In case of pre-treatment characteristics with multiple measurements per subject before the start of treatment (laboratory assessments, vital signs), the last value prior to or on the first day of treatment will be considered the baseline measurement.

8.4. Treatment Administration

Total cumulative dose, dose intensity and relative dose intensity, administration times, time on treatment, cycle delays, dose reductions and omissions will be described using standard tables detailed in Appendix I.

Total cumulative dose, expressed in mg, is the sum of all the study drug doses from the first cycle until last cycle, including the dose received in the last cycle.

Patients will be considered to be on-treatment for the duration of their treatment and for 30 days after the last treatment dose. If the patient starts any new antitumor therapy outside this clinical trial or dies within 30 days of the last treatment dose, the date of administration of this new therapy or the date of death will be considered the date of treatment discontinuation.

However, as a convention, the duration of the last cycle is considered to be 21 days (instead of 30 days) for dose intensity calculation purposes.

Intended dose intensity is the planned dose per cycle divided by the planned number of weeks per cycle. Absolute dose intensity is the actual cumulative dose divided by the number of weeks of treatment. Relative dose intensity (%) is the ratio of absolute dose intensity divided by the intended dose intensity.

The item of the CRF «Infusion delayed: yes/no» will be used to calculate the delayed cycles. For those cycles considered as delayed by the Investigator, the delay (days) will be calculated as follows:

$$\text{Delay} = \text{Date of current drug administration} - \text{Date of previous drug administration} - 21$$

The infusion of the first cycle will be excluded from all calculations regarding cycle delays and modifications.

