5.2 ADMINISTRATION OF STUDY MEDICATION

PM060184 at a dose of 9.3 mg/m² (dose can be rounded to the first decimal point) will be administered as a 30-minute i.v. infusion via a central or peripheral venous catheter, on Day 1 and Day 8 q3wk (three weeks=one treatment cycle).

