5.3 CRITERIA FOR TREATMENT CONTINUATION

Patients will be treated with additional cycles of PM060184 until disease progression (PD), as long as none of the following occur: unacceptable toxicity, and/or patient refusal to receive further study treatment, and/or Investigators’ decision.

The administration of subsequent cycles (after Cycle 1) should be delayed if criteria for treatment continuation ([Table 4](#)) are not met on the corresponding Day 1. If criteria for treatment continuation are not met on Day 8 (i.e. seven days after the first dose administration of a cycle) of any cycle, administration should be omitted instead of delayed.

Table 4. Criteria for treatment continuation.

Abnormality	Day 1 ^a	Day 8
ANC	$\geq 1.5 \times 10^9/L$	$\geq 1.0 \times 10^9/L$
Platelets	$\geq 100 \times 10^9/L$	$\geq 75 \times 10^9/L$
Hemoglobin ^b	≥ 9 g/dL	≥ 9 g/dL
Total bilirubin	$\leq 1.5 \times$ ULN (grade 1)	
AST/ALT	Grade ≤ 1 ^c	Grade ≤ 2
Calculated CrCL (Cockcroft-Gault formula)	≥ 40 mL/min	≥ 30 mL/min
Peripheral sensory/motor neuropathy	Grade ≤ 2	Grade ≤ 2
Nausea/vomiting, fatigue, anorexia	Grade ≤ 2	Grade ≤ 2
Other non-hematological drug-related AEs (except metabolic abnormalities ^d)	Grade ≤ 1	Grade ≤ 2

^a Except Day 1 of Cycle 1.

^b If hemoglobin levels are not met, the Investigator will have the option of giving the patient a transfusion instead of delaying (on Day 1) or omitting (on Day 8) a dose.

^c Grade ≤ 2 , for patients with liver metastases and with AST and/or ALT levels $\leq 5.0 \times$ ULN at registration.

^d Any grade accepted for increased GGT. Up to grade 4 accepted for non-symptomatic metabolic abnormalities (e.g., sodium, magnesium, potassium, calcium).

AE, adverse event; ALT, alanine aminotransferase; ANC, absolute neutrophil count; AST, aspartate aminotransferase; CrCL, creatinine clearance; GGT, gamma-glutamyltransferase; ULN, upper limit of normal.

A maximum delay of 15 days is allowed for the recovery of patients from toxicity. If toxicities have not recovered after this period, the patient should discontinue treatment. Exceptionally, in case of obvious clinical benefit, the patient can remain on treatment but only after discussion and mutual agreement with the Sponsor, and upon recovery of all parameters according to the aforementioned criteria.

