5.4 DOSE REDUCTION

Dose can be reduced on the basis of the worst toxicity (drug-related adverse event [AE]) occurring since the previous dose (e.g., Day 1 or Day 8 of any cycle except for Day 1 of Cycle 1). The PM060184 dose reduction schedule is described in [Table 5](#), and criteria according to toxicity in [Table 6](#) and [Table 7](#).

Table 5. PM060184 dose reduction levels.

Dose level	PM060184
-1	7.5 mg/m ²
-2	6.0 mg/m ²

Table 6. Criteria for PM060184 dose reduction for hematological toxicity.

Abnormality	Nadir value	PM060184
ANC	< $0.5 \times 10^9/L$ with fever ($\geq 38.5^\circ C$)/infection, or < $0.5 \times 10^9/L$ for ≥ 3 days	Reduce one dose level
Platelet count	< $50 \times 10^9/L$, with significant bleeding, or < $25 \times 10^9/L$	Reduce one dose level

A second occurrence of the aforementioned toxicities should lead to a further dose reduction (i.e., dose level -2). No more than two dose reductions will be allowed.

ANC, absolute neutrophil count.

Table 7. Criteria for PM060184 dose reduction for non-hematological toxicity.

Abnormality	Worst NCI-CTCAE grade	PM060184
Peripheral sensory/motor neuropathy	≥ 3	Reduce one dose level
Prolonged peripheral sensory/motor neuropathy ^a	≥ 2	Reduce one dose level
Abdominal pain (if reoccurring after the first administration)	≥ 3	Reduce one dose level
Nausea/vomiting despite adequate antiemetic treatment	≥ 3	Reduce one dose level
Fatigue (if reoccurring or persistent after Cycle 2)	≥ 3	Reduce one dose level
Other treatment-related AEs according to the Investigator's criteria	≥ 3	Reduce one dose level

A second occurrence of these toxicities should lead to a further dose reduction (i.e., reduction to dose level -2). No more than two dose reductions will be allowed.

^a Lasting more than two cycles.

AE, adverse event; NCI-CTCAE, National Cancer Institute Common Terminology Criteria for the Classification of Adverse Events.

No more than two dose reductions per patient will be allowed in the course of this clinical trial. Patients requiring more dose reductions should discontinue treatment, except in the event of obvious clinical benefit, in which case, treatment may continue after discussion and mutual agreement with the Sponsor.

No dose escalations will be allowed in this clinical trial.

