12.1.2. Cycle Delays

Listing 12.1.2 Delays.

Patient id.	Delayed cycle	Delayed cycle start date	Previous cycle	Previous cycle start date	Calculated dose delay (days)	Reason for dose delay	Specify reason for dose delay

Table 12.1.3 Number of patients and cycles with dose delay, any relationship.

	N	%
Patients treated		
Patients with any dose delay		
Cycles administered		
Cycles susceptible to be delayed* ¹		
Cycles with dose delay* ²		
Patients with		
No cycles delayed		
1 cycle delayed		
2 cycles delayed		
≥ 3 cycles delayed		

(*¹) All cycles excluding first cycle. (*²) Denominator= Number of cycles susceptible to be delayed.

Table 12.1.4 Number of patients and cycles with dose delay according to relationship with study treatment.

	Treatment-related* ²		Non-treatment-related	
	N	%	N	%
Patients with				
No cycles delayed				
1 cycle delayed				
2 cycles delayed				
≥ 3 cycles delayed				
Cycles with dose delay* ¹				

(*¹) Denominator= Number of cycles susceptible to be delayed. (*²) Hematological reason, non-hematological reason or both.

Table 12.1.5 Number of patients and cycles with dose delay according to relationship with study treatment.

Reasons for treatment-related delays	N	%
Cycles with dose delays*		
Hematological		
Non-hematological		
Both		
Patients with dose delays		
Hematological		
No cycles delayed		
1 cycle delayed		
2 cycles delayed		
≥ 3 cycles delayed		
Non-hematological		
No cycles delayed		
1 cycle delayed		
2 cycles delayed		
≥ 3 cycles delayed		
Both		
No cycles delayed		
1 cycle delayed		
2 cycles delayed		
≥ 3 cycles delayed		

(*) Denominator= Number of cycles susceptible to have a delay.

Table 12.1.6 Length of dose delay.

Length of delay	Median (range)	Treatment-related* ²		Non-treatment-related		Total	
		N	%	N	%	N	%
Length of delay* ¹							
≤ 7 days							
>7 days and ≤14 days							
> 14 days							

(*¹) Denominator= Number of cycles susceptible to be delayed. (*²) Hematological reason, Non-hematological reason or both.

The distribution of delays according to the cycle administered will be studied by means of counts and percentages. The reasons for cycle delay will be detailed, specifying how many were due to treatment or not.

Listing 12.1.7 Cycle delays due to AEs.

Patient id.	Cycle	Preferred term code	AE reported (verbatim)	Grade	Relationship	Onset date	Resolved date	No. of days with delay	Action taken	Significant consequences

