12.1.4. Dose Reductions

All dose reductions should be considered and described, specifying the reason for reduction (hematological toxicity, non-hematological toxicity or other causes).

Listing 12.1.11 Dose reductions.

Patient id.	Cycle	Day	Cycle start date	Previous dose	Reduced dose	Reason for dose reduction	Dose reduction Spec.

Table 12.1.12 Number of patients and infusions with dose reduction, any relationship.

	N	%
Patients treated		
Patients with any dose reduced		
Cycles susceptible to be reduced in dose		
Patients with		
No dose reductions		
1 cycle with dose reduced		
2 cycles with dose reduced		
≥ 3 cycles with dose reduced		
Cycles administered		
Cycles susceptible to have any dose reduced* ¹		
Cycles with dose reduced * ²		
Cycles with dose reduced (Treatment-related)* ²		

(*¹) All cycles. (*²) Denominator= Number of cycles susceptible to have a dose reduction.

Table 12.1.13 Number of patients and cycles with dose reduction according to the relationship.

	Treatment-related* ²		Non-treatment-related	
	N	%	N	%
Patients with				
No dose reductions				
1 cycle with dose reduced				
2 cycles with dose reduced				
≥ 3 cycles with dose reduced				
Cycles with dose reduction* ¹				

(*¹) Denominator= Number of cycles susceptible to be delayed. (*²) Hematological reason, non-hematological reason or both.

Table 12.1.14 Number of patients and cycles with dose reduction according to the reason of the relationship.

Reasons for treatment-related reduction	N	%
Cycles with dose reduction*		
Hematological		
Non-hematological		
Both		
Patients with dose reduction		
Hematological		
No dose reductions		
1 cycle with dose reduced		
2 cycles with dose reduced		
≥ 3 cycles with dose reduced		
Non-hematological		
No dose reductions		
1 cycle with dose reduced		
2 cycles with dose reduced		
≥ 3 cycles with dose reduced		
Both		
No dose reductions		
1 cycle with dose reduced		
2 cycles with dose reduced		
≥ 3 cycles with dose reduced		

(*) Denominator= Number of cycles susceptible to have a dose reduction.

Listing 12.1.15 Dose reductions due to AEs.

Patient id.	Total no. of cycles	Cycle	Preferred term code	AE reported (verbatim)	Grade	Relationship	Onset date	Resolved date	Action taken	Significant consequences

AEs with action = ‘Dose reduced’, ‘Dose omitted/ reduced’, ‘Dose delayed/reduced’ or ‘Dose delayed/ omitted/ reduced’.

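### SAP Table 12.1.13 reports dose reductions over the delay denominator, which leaves out Cycle 1, and the Cycle 1 exclusion in SAP 8.4 is ambiguous when each cycle has two infusions

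*SAP*

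**What the plan says.** **Dosing and when it can change.** Protocol 5.2 gives PM060184 "on Day 1 and Day 8 q3wk (three weeks=one treatment cycle", so each cycle has two infusions. Protocol 5.4 bases a reduction on toxicity since the previous dose and describes where it can apply as "Day 1 or Day 8 of any cycle except for Day 1 of Cycle 1". Protocol 5.3 says that if the continuation criteria fail on Day 8 "of any cycle, administration should be omitted instead of delayed". Day 8 of Cycle 1 can therefore be reduced or omitted; only Day 1 of Cycle 1 is exempt.

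**General rule in the SAP.** SAP 8.4: "The infusion of the first cycle will be excluded from all calculations regarding cycle delays and modifications".

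**Denominators in the SAP tables.**
- Table 12.1.3 (delays) defines cycles susceptible to delay as "All cycles excluding first cycle".
- Table 12.1.12 (reductions) defines cycles susceptible to reduction as all cycles and divides by that number.
- Table 12.1.13 (reductions by relationship) carries this footnote on its cycle row: "Denominator= Number of cycles susceptible to be delayed. (*²) Hematological reason, non-hematological reason or both".
- Table 12.1.14 (reasons for treatment-related reductions) returns to the reduction denominator.
- Table 12.1.9 (omissions) divides by the infusions that could be omitted and does not say which these are.

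**The concern.** A denominator built for delays suits delays. Cycle 1 has no earlier cycle to be late from, so leaving it out is right there. It does not suit reductions, because Cycle 1 contains a dose that can be reduced. Table 12.1.13 nevertheless uses the delay base, between two tables that do not. Cycles with a treatment-related reduction appear in both Table 12.1.12 and Table 12.1.13, so a reader of the study report would find two percentages for the same count.

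The sentence in 8.4 raises the same question more generally. It speaks of one infusion in a cycle that has two and covers modifications as well as delays. If a programmer takes it to mean all of Cycle 1, reductions and omissions at the second dose, the earliest sign of intolerance, leave the summary rates. Dose reductions due to treatment-related adverse events belong to the safety endpoint in Protocol 9.2 and SAP 3.3, so the tables should be unambiguous, although they are only descriptive.

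**Working it through.** The documents state no expected reduction or omission rate, so there is no planned figure to reproduce. The check compares the rules and then sizes the effect under stated assumptions.

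**Step 1: the base.** Let N be the number of treated patients and c the mean number of cycles per treated patient. Every treated patient has one Cycle 1.
- All cycles (Table 12.1.12): N × c.
- Cycles without Cycle 1 (Table 12.1.3, carried into Table 12.1.13): N × c − N = N × (c − 1).

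If R cycles have a reduction and Cycle 1 is counted in R, the ratio of the Table 12.1.13 percentage to the Table 12.1.12 percentage is [R / N(c − 1)] / [R / Nc] = c/(c − 1). It depends on neither N nor R. A patient who stops after Cycle 1 with a reduced Day 8 dose adds 1 to the numerator and 0 to the denominator.

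**Step 2: numbers.** The documents do not give c, so a range is shown. N = 60 is the planned number of evaluable patients and serves only as a scale; the tables use all treated patients.

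| Assumed c | All cycles | Without Cycle 1 | Factor |
|---|---|---|---|
| 2 | 120 | 60 | 2.00 |
| 3 | 180 | 120 | 1.50 |
| 4 | 240 | 180 | 1.33 |
| 6 | 360 | 300 | 1.20 |

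For example, 18 reduced cycles at c = 3 read 18/180 = 10% on the reduction base and 18/120 = 15% on the delay base.

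**Step 3: the two readings of 8.4.** Take N = 60 and c = 4, so 60 first cycles and 180 later ones. The reduction rates are assumed.

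| Rate in Cycle 1 / later | Reduced cycles | All cycles in both | All reductions over delay base | Cycle 1 dropped from both |
|---|---|---|---|---|
| 10% / 10% | 6 + 18 = 24 | 24/240 = 10.0% | 24/180 = 13.3% | 18/180 = 10.0% |
| 20% / 5% | 12 + 9 = 21 | 21/240 = 8.8% | 21/180 = 11.7% | 9/180 = 5.0% |
| 5% / 20% | 3 + 36 = 39 | 39/240 = 16.25% | 39/180 = 21.7% | 36/180 = 20.0% |

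The fourth column is Table 12.1.13 with Cycle 1 reductions counted. The last column is the strict reading of 8.4. Dropping Cycle 1 from both numerator and denominator can lower the rate, raise it or leave it unchanged. In each row it loses the Cycle 1 events: 6 of 24, 12 of 21 and 3 of 39.

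**Step 4: consistency.** If 8.4 excludes only Day 1 of Cycle 1, it agrees with Protocol 5.4 and with Table 12.1.12, because Cycle 1 still holds one reducible dose. If it excludes all of Cycle 1, it conflicts with the all-cycles definition in Table 12.1.12. In neither case does a delay denominator fit a reduction table.

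**The case against.** A reader might infer that modification rates in general will be wrong, that the SAP contradicts the protocol, or that Cycle 1 Day 8 events will vanish from the report. The documents do not support any of these.

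- The singular in 8.4 can mean the initial infusion, which is exactly the protocol's exemption. On that reading no Day 8 event is lost. The delay formula in the same section does not settle the matter, since it too refers to drug administrations without distinguishing Day 1 from Day 8.
- Protocol 5.3 and 5.4 are dosing rules. Protocol 9.6 says that delays and reductions will be considered but sets no denominator, so there is no tabulation rule to contradict.
- Table 12.1.9 does not itself exclude Cycle 1, and Listings 12.1.8, 12.1.10, 12.1.11 and 12.1.15 show omissions and reductions by cycle. A rule about calculations does not remove listed events.
- The footnote repeats that of delay Table 12.1.4 and looks like a carry-over. It governs one row; the patient counts in Table 12.1.13 are unaffected, and Table 12.1.12 already gives the treatment-related rate on the right base.
- SAP 8.16 places calculation conventions in a separate document that is not available here.

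All of this stands, and it narrows the point. It does not rescue the footnote, which is a stated rule and wrong for reductions on either reading of 8.4. Nor does it make 8.4 clear: two programmers could build different tables from it.

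**Conclusion.** The point holds in a limited form and is minor. What is certain is that the cycle row of Table 12.1.13 uses the wrong denominator and will disagree with Table 12.1.12. With Cycle 1 reductions in the numerator the overstatement is c/(c − 1), or 1.2 to 2 times over an assumed 6 down to 2 cycles per patient. The factor rests only on the mean number of cycles, which the documents do not give; the percentages in the examples also rest on assumed event rates.

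The sentence in 8.4 is ambiguous rather than demonstrably wrong, and the omission rate in Table 12.1.9 is undefined rather than biased. Cumulative dose is summed from the first cycle (SAP 8.4), so dose intensity still reflects a reduced or omitted Cycle 1 Day 8 dose. PFS3 and the futility rule do not use these tables.

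**What to change.** Make three edits to the SAP:

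1. **Table 12.1.13 footnote:** replace the delay denominator with the reduction denominator already used in Tables 12.1.12 and 12.1.14.
2. **Section 8.4:** state that Cycle 1 is excluded from cycle-delay calculations, that only Day 1 of Cycle 1 is excluded from reduction and omission calculations, and that Day 8 of Cycle 1 is counted for both.
3. **Table 12.1.9:** define the infusions that can be omitted so that Day 8 of Cycle 1 is included.

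The cost is one footnote, one sentence and one definition. No new data are needed, and neither the protocol nor any efficacy analysis changes. If the separate conventions document already settles the meaning of 8.4, it should be brought into line with the new wording.

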8.5. Subsequent Therapy

A table summarizing the subsequent therapies received after treatment discontinuation will be shown.

8.6. Pharmacokinetic Analyses

This analysis will be detailed in a separate document.

8.7. Pharmacogenetic Analyses

This analysis will be detailed in a separate document.

8.8. Pharmacogenomic Analyses

This analysis will be detailed in a separate document.

8.9. Metabolomics (Biomarkers)

This analysis will be detailed in a separate document.

8.10. Imputation of Incomplete Dates

The dates of certain historical or current clinical activities are key component for statistical analysis. An incomplete date results from a missing day, month or year; in that case, the missing figure can be imputed allowing for the calculation of variables, such as duration and time to certain event. However, when all of them, day, month and year are missing no imputation will be done.

Before registration/treatment start

If the day of a month is unknown, then the imputed day will be the 15th of the month; if the month is also unknown, then the imputed date will be the 1st of July. This assumption will only be valid if the imputed date occurs earlier than the first dose administration date; otherwise the imputed date will be the first day of the month in which the first dose was administered (i.e. 01/ first dose administration month date/year).

Between treatment start and end of treatment

All date variables during treatment for which information is needed and is not fully available, for example AEs or concomitant medications, will be subjected to imputation by means of SAS programming. If the day of a date is unknown then the imputed day will be the 1st of the month, if the month and/or year are also unknown then the imputed date will be the 1st of January. This assumption will be valid if the imputed date is earlier than the treatment start date; otherwise, the imputed date will be the treatment start date.

After end of treatment

To ensure the most conservative approach for the time-to-event variables (i.e., DR, PFS and OS), which can be affected by missing values, the following rules will be implemented: if the day of a date is unknown then the imputed day will be the 1st; if the month is also unknown, then the imputed date will be the 1st of July. This assumption will be valid if the imputed date occurs later than the last drug administration date; otherwise the imputed date will be the date of the last drug administration plus the predefined cycle length (i.e., 21 days if PM060184), except if the patient dies before, in which case the date of death minus 1 will be used.

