8.2 SAFETY

Patients will be evaluable for safety if they receive at least one (complete or incomplete) dose of PM060184.

Safety will be evaluated by clinical examinations, analysis of vital signs, clinical assessment of AEs, changes in the analytical parameters (hematological and biochemical), and any other analyses that may be considered necessary.

All treatment-related AEs must be followed-up—even if the administration of PM060184 has finalized—until the AE or its sequelae have resolved or stabilized at an acceptable level to the Investigator and the Sponsor. AEs will be graded according to the National Cancer Institute Common Terminology Criteria for Adverse Events (NCI-CTCAE v.4), and will be coded using the Medical Dictionary for Regulatory Activities (MedDRA).

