11.1.9. Signs and Symptoms at Baseline

Table 11.1.29 Signs and symptoms at baseline*.

	N	%
No. of signs and symptoms per patient		
0		
1		
2		
≥ 3		
Median (range)		
Mean (StD)		
No. of disease related signs and symptoms per patient		
0		
1		
2		
≥ 3		
Median (range)		
Mean (StD)		

(*) AEs with onset day previous to first administration of the study treatment.

Table 11.1.30 Signs and symptoms at baseline.

MedDRA SOC/PT*	N	Grade 1		Grade 2		Grade 3		Grade 4		Grade 1/4	
		N	%	N	%	N	%	N	%	N	%
Constipation											
Diarrhoea											
Dyspnea											
Pain											
...											

(*) Sorted by frequency.

Table 11.1.31 Disease related signs and symptoms at baseline.

MedDRA SOC/PT*	N	Grade 1		Grade 2		Grade 3		Grade 4		Grade 1/4	
		N	%	N	%	N	%	N	%	N	%
Constipation											
Diarrhoea											
Dyspnea											
Pain											
...											

(*) Sorted by frequency.

Listing 11.1.32 Signs and symptoms at baseline.

Patient	Sign/symptom	Grade	Onset date	Relationship	Treated

(*) Those events with grade ≥ 2 or with relationship='Prior tumor treatment' will be highlighted.

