12.2. Adverse Events

As far as all toxicities are concerned, the NCI-CTCAE v.4 grade will be used wherever an NCI-CTCAE grading exists. Otherwise, the severity will be noted. As a convention, the term «Grade» will always be used. Toxicities will be described according to the worst NCI-CTCAE grade or, for toxicities which do not form the subject of NCI-CTCAE classification, according to the worst severity, as described in NCI-CTCAE.

AEs will be described in this section; treatment-related events (stated as related to the study drug or of unknown relationship) will be tabulated. AEs regardless relationship will be tabulated in two different ways as any AE reported or as treatment emergent AEs (excluding AEs present before drug administration and without increase in severity grade along the treatment).

Type of toxicity and worst grade or severity by cycle and by patient will be summarized according to the Preferred Term coded with MedDRA. Tables will be organized per category of events using System Organ Class of MedDRA.

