12.2.1. Display of Adverse Events

Table 12.2.1 Summary of AEs.

Category*	N (%)
Any AE	
Any drug-related AE	
Any grade 3/4 AE	
Any grade 3/4 drug-related AE	
Any treatment emergent AE* ²	
Any SAE in clinical database	
Any drug-related SAE in clinical database	
Any grade 3/4 SAE in clinical database	
Any grade 3/4 drug-related SAE in clinical database	
Deaths associated with AEs	
Deaths associated with drug-related AEs	
Treatment discontinuations associated with AEs	
Treatment discontinuations associated with drug-related AEs	

(*) Drug-related: AEs drug-related and unknown relationship.

(*²) excluding AEs present before drug administration and without increase in severity grade along the treatment.

Table 12.2.2 Treatment-related AEs. Worst grade by patient.

SOC	Preferred Term	Grade 1		...	Grade 4		All*	
		N	%		N	%	N	%
Blood and lymphatic system disorders	Anaemia Not Otherwise Specified (NOS)							
	...							
	...							
Cardiac disorders	Neuropathy peripheral							
	...							

(*) Any grade.

Table 12.2.3 Treatment-related AEs. Worst grade by cycle.

SOC	Preferred Term	Grade 1		...	Grade 4		All*	
		N	%		N	%	N	%
Blood and lymphatic system disorders	Anaemia NOS							
	...							
	...							
Cardiac disorders	Neuropathy peripheral							
	...							

(*) Any grade.

Table 12.2.4 Adverse Event regardless of relationship. Worst grade by patient.

SOC	Preferred Term	Grade 1		...	Grade 4		All*	
		N	%		N	%	N	%
Blood and lymphatic system disorders	Anaemia NOS							
	...							
	...							
Cardiac disorders	Neuropathy peripheral							
	...							

(*) Any grade.

Table 12.2.5 Adverse Event regardless of relationship. Worst grade by cycle.

SOC	Preferred Term	Grade 1			...	Grade 4		All*	
		N	%	...	N	%	N	%	
Blood and lymphatic system disorders	Anaemia NOS								
	...								
	...								
Cardiac disorders	Neuropathy peripheral								
	...								

(*) Any grade.

Table 12.2.6 Treatment emergent AEs. Worst grade by patient.

SOC	Preferred Term	Grade 1			...	Grade 4		All*	
		N	%	...	N	%	N	%	
Blood and lymphatic system disorders	Anaemia NOS								
	...								
	...								
Cardiac disorders	Neuropathy peripheral								
	...								

(*) Any grade.

Table 12.2.7 Treatment emergent AEs. Worst grade by cycle.

SOC	Preferred Term	Grade 1			...	Grade 4		All*	
		N	%	...	N	%	N	%	
Blood and lymphatic system disorders	Anaemia NOS								
	...								
	...								
Cardiac disorders	Neuropathy peripheral								
	...								

(*) Any grade.

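### SAP 8.10 has the on-treatment date-imputation test backwards: no partial date can fall after Day 1, and some on-treatment AE onsets become pre-dose

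*SAP*

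**What the plan says.** SAP 8.10 has three rules for incomplete dates, one per study period. The middle rule covers treatment start to end of treatment and applies to "All date variables during treatment for which information is needed and is not fully available, for example AEs or concomitant medications". It sets a missing day to the 1st of the month, and a date that also lacks the month and/or year to 1 January. The check on that value is that it is "valid if the imputed date is earlier than the treatment start date; otherwise, the imputed date will be the treatment start date". A date missing day, month and year is not imputed.

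The rule for dates before treatment keeps an imputed date only if it precedes first dose. The rule for dates after treatment reads: "This assumption will be valid if the imputed date occurs later than the last drug administration date".

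Two other parts of the SAP depend on where an AE onset falls relative to first dose:

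- The footnote to Table 11.1.29 (SAP 11.1.9) defines baseline signs and symptoms as "AEs with onset day previous to first administration of the study treatment".
- SAP 12.2 defines treatment-emergent AEs by "excluding AEs present before drug administration and without increase in severity grade along the treatment". This feeds Table 12.2.6 ("Treatment emergent AEs. Worst grade by patient"), Table 12.2.7, Listings 12.2.12 and 12.2.13, and one row of Table 12.2.1.

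**The concern.** A validity check should hold an imputed date inside its own period. The pre-treatment and post-treatment rules do so. The on-treatment rule keeps dates that lie outside its period and overwrites those that lie inside it, even when the recorded month is plainly later than first dose.

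There are three consequences:

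1. **Onset moved to before first dose.** This happens when the day is missing and the month is that of first dose (unless dosing began on the 1st), or when only the year of first dose is known (unless dosing began on 1 January). A real on-treatment AE is then classed as baseline and drops out of the treatment-emergent outputs unless its grade later rises. Toxicity is understated.
2. **Onset reset to Day 1.** This happens to a missing-day onset in any later month. The AE stays treatment-emergent, but its timing and duration are wrong.
3. **Stop dates moved too.** The rule covers every on-treatment date variable, so a partial stop date goes to Day 1 or earlier and can precede its own onset.

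The safety profile is a stated secondary objective (Protocol 3, SAP 3.2).

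**Working it through.** The plan gives no figure to reproduce. The check is to trace the rule and then count outcomes.

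**Formula.** Let *i* be the imputed date and *s* the first dose. As written, the final date is *i* if *i* < *s*, otherwise *s*, which is min(*i*, *s*). With the condition reversed it is max(*i*, *s*).

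**Trace, first dose 10 January:**

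| Recorded | *i* | As written | Reversed |
|---|---|---|---|
| Onset in January, day missing | 1 Jan | 1 Jan (9 days pre-dose) | 10 Jan |
| Onset in March, day missing | 1 Mar | 10 Jan (Day 1) | 1 Mar |
| Onset, same year only | 1 Jan | 1 Jan (9 days pre-dose) | 10 Jan |
| Onset 20 Feb complete; stop in March, day missing | 1 Mar (stop) | stop 10 Jan, 41 days before onset | stop 1 Mar |

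**Counting.** Inputs:

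- Assumed dosing of 42, 84 or 168 days.
- The 30-day tail from SAP 8.4, where patients count as "on-treatment for the duration of their treatment and for 30 days after the last treatment dose". This gives D = 72, 114 or 198 days.
- First dose equally likely on each of 365 days, and onset equally likely on each of days 0 to D. Both are assumptions. There are 365 × (D + 1) combinations.

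*Day missing.* An onset goes pre-dose when it falls in the first-dose month and dosing did not begin on the 1st. A month of L days contributes L(L − 1)/2 combinations. Over the year that is 7 × 465 + 4 × 435 + 378 = 5,373.

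- D = 72: 5,373 / (365 × 73) = 5,373 / 26,645 = 20.2%
- D = 114: 5,373 / (365 × 115) = 5,373 / 41,975 = 12.8%
- D = 198: 5,373 / (365 × 199) = 5,373 / 72,635 = 7.4%

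All other dates land on Day 1: 79.8%, 87.2% and 92.6%.

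*Day and month missing.* An onset goes pre-dose when it falls in the calendar year of first dose and dosing did not begin on 1 January. With W = D + 1, the count is W(W + 1)/2 + (364 − W)W.

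- D = 72: (2,701 + 21,243) / 26,645 = 89.9%
- D = 114: (6,670 + 28,635) / 41,975 = 84.1%
- D = 198: (19,900 + 32,835) / 72,635 = 72.6%

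**Mean backward shift from true onset, by full enumeration (days):**

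| D | Day missing: written | Reversed | Day and month missing: written | Reversed |
|---|---|---|---|---|
| 72 | 38.1 | 12.6 | 184.4 | 33.6 |
| 114 | 58.3 | 13.4 | 188.0 | 51.0 |
| 198 | 99.8 | 13.9 | 200.1 | 80.9 |

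As written, no date falls after Day 1. Reversed, none falls before first dose. Neither result depends on the assumptions.

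**Sensitivity.** With onset windows of 21, 42, 84 or 168 days and first doses spread over 730 days, the pre-dose share is 64%, 35%, 18% or 9% with the day missing, and 97%, 94%, 88% or 77% with the month missing.

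**The case against.** The strongest reply is that this is a one-word slip, earlier for later. The subsection heading and both neighbouring rules show the intent, and SAP 8.16 places calculation conventions in a separate document that is not supplied, so faulty programming cannot be shown. That is probably right about the cause. But SAP 8.10 says the imputation is done by SAS program, a literal program would misdate events, and a correct conventions document would contradict the SAP. The text needs correcting either way.

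The second reply is that the reach is narrow, and much of this stands:

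- The SAP shells include no AE-duration or time-to-AE-onset analysis. The onset-day and recovery-time outputs (Tables 12.4.15 and 12.4.16) concern laboratory values. Consequences 2 and 3 therefore touch mainly patient listings, and the SAP does not say whether those show raw or imputed dates. By-cycle tables change only if cycle is derived from onset date, which the SAP does not say.
- SAP 12.2 does not say that presence before dosing is derived from an imputed onset, and baseline conditions are collected separately as screening AEs (Protocol, Schedule of Assessments and Procedures, note 13). Misclassification is therefore plausible rather than certain. The Table 11.1.29 footnote does, however, use onset day.
- The shares move a great deal with the assumed window. Nothing shows how often an on-treatment AE, reported at least every cycle, would lack its month.

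**Conclusion.** The concern holds. Read as written, the rule returns the earlier of the imputed date and first dose, and nothing else in the supplied documents corrects it. That no partial on-treatment date can fall after Day 1 follows from the text alone. The percentages and mean shifts are per partial date, rest on assumed dosing durations and uniform dates, and are illustrative. The number of partial dates, and so the practical effect, is unknown.

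The firmest consequence is the first: on-treatment AEs can move from the treatment-emergent outputs to the baseline table. Complete dates, wholly missing dates, tables defined by drug relationship or as any AE reported, and PFS3 are not shown to be affected. This is a definite error in a safety rule that should be corrected. It does not threaten the primary analysis.

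**What to change.** Replace the condition in the on-treatment rule of SAP 8.10 with:

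> For onset and start dates, the imputed date stands if it is on or after the treatment start date; otherwise the treatment start date is used.

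Then add:

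> This floor applies to onset and start dates only. An imputed stop date must agree with any known month and year, must not precede its own onset, and is not capped at end of treatment.

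Stop dates are left uncapped because related AEs are followed after discontinuation until "resolved or stabilized at an acceptable level to the Investigator and the Sponsor" (Protocol 8.2; Protocol 8.5.1 is to the same effect).

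Two details should be settled in the same edit. First, give a fallback for a stop date whose default falls before onset; for onset 20 March and a stop recorded only as March, the default of 1 March does. The onset date is a natural choice. Second, say which year goes with 1 January when the year is unknown. Any separate conventions document should be checked against the corrected text.

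The cost is two or three SAP sentences and a small programming correction. The trade-off is that an AE with a partial date in the first-dose month that truly began shortly before dosing will be counted as starting on Day 1, which is the cautious direction for safety reporting.
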